14.3 Stratification Factors

N/A

14.4 Analysis of Secondary Endpoints

Phase I:

Pharmacokinetic parameters will be analyzed to determine whether pharmacologically significant drug interactions are present between everolimus and pazopanib. The concentration of everolimus in whole blood and plasma will be determined using a validated assay involving high performance liquid chromatography with electrospray ionization mass spectrometric detection. Time points will be determined as the difference between the midpoint of the blood collection interval and starting time of dose administration. Concentration-time profiles will be analyzed by noncompartmental methods and/or nonlinear least squares regression using Professional version 4.0.1 software package (Pharsight Corp., Cary, NC). Pharmacokinetic parameters and

variables will be calculated according to standard equations. Descriptive summaries of PK parameters (C_{trough}, T_{1/2} and C_{max}) will be provided by dose cohort.

Secondary

Secondary endpoints will evaluate safety, progression-free survival (PFS), overall survival (OS) and duration of response. Duration of response is calculated for objective responders and defined as the time in months from the first observation of a response (e.g., the first time that the appropriate RECIST 1.1 criteria was observed for confirmed responders) to the first documented progression or death due to any cause, whichever occurs first. Duration of response is censored at the date of last disease evaluation for patients who are known to be alive and who have not relapsed after a CR or PR.

Progression-free survival is calculated as the months between registration and documented PD as determined by RECIST 1.1, or death due to any cause, whichever occurs first. Overall survival is defined as the time in months from registration to death due to any cause or, censored at the date last known alive. Patients alive without disease progression will be censored at the date of last disease evaluation. Time to event data will be estimated with the Kaplan-Meier method. Efficacy will further be described by 4- and 12-month PFS and OS rates along with 90% CIs. Descriptive statistics will be used to characterize the disease and previous treatment features as well as the details of protocol therapy.

Toxicity

All patients who receive treatment will be included in toxicity analyses. A summary of the incidence of all treatment-related grade 3-5 toxicities will be provided as maximum grade by toxicity type and body system. Any other information collected (e.g. severity or relatedness to study medication) will be listed as appropriate. Overall maximum grade 3 or higher treatment-related toxicity rates in all treated patients will be calculated. The table below shows the 90% confidence intervals for 0, 2, 4, and 6 patients with grade 3 or higher toxicity in a total of 29 treated patients.

Observed Number of Patients with Grade \geq 3 Toxicity	Grade \geq 3 Toxicity Rate	90% Confidence Interval for True but Unknown Grade \geq 3 Toxicity Rate
0	0.0%	(0.0%, 9.8%)
2	6.9%	(1.3%, 20.2%)
4	13.8%	(4.9%, 28.9%)
6	20.7%	(9.4%, 36.8%)

Exploratory

Relevant somatic and germline alterations will be identified by adaptation and modification of discovery-oriented algorithms in common use at the Broad Institute and MSKCC. We will also apply a series of computational algorithms that predict neutral, detrimental or activating variants. Upon completion, we will deliver a list of somatic and germline variants that perturb cancer genes and associated cellular pathways, associated with response to therapy in this cohort. Relevant associations between mutation status and treatment outcome will be assessed on an exploratory basis, and relevant targeted sequencing may be performed in non-responders to further understand the association between response to study therapy and somatic alterations.

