2. BACKGROUND

2.1 Study Agent(s)

2.1.1 Everolimus

Everolimus, a novel oral derivative of rapamycin, has been in clinical development since 1996 as an immunosuppressant in solid organ transplantation and has obtained marketing authorization (Certican®) for prophylaxis of rejection in renal and cardiac transplantation in a number of countries, including the majority of the European Union. Everolimus has been in development for patients with various malignancies since 2002. Everolimus was FDA approved in 2009 (Afinitor®) for the treatment of kidney cancer that has progressed after sunitinib or sorafenib. Everolimus is being investigated as an anticancer agent based on its potential to act:

- Directly on the tumor cells by inhibiting tumor cell growth and proliferation
- Indirectly by inhibiting angiogenesis leading to reduced tumor vascularity (via potent inhibition of tumor cell HIF-1 activity, VEGF production and VEGF-induced proliferation of endothelial cells). The role of angiogenesis in the maintenance of solid tumor growth is well established, and the mTOR pathway has been implicated in the regulation of tumor production of proangiogenic factors as well as modulation of VEGFR signaling in endothelial cells.

At weekly and daily schedules and at various doses explored, RAD001 is generally well tolerated. The most frequent adverse events (rash, mucositis, fatigue and headache) associated with everolimus therapy are manageable. Non-infectious pneumonitis has been reported with mTOR inhibitors but is commonly low-grade and reversible.

2.1.1.1 mTOR pathway and mechanism of action

At cellular and molecular level everolimus acts as a signal transduction inhibitor. Everolimus selectively inhibits mTOR (mammalian target of rapamycin), a key and a highly conserved serine-threonine kinase, which is present in all cells and is a central regulator of protein synthesis and ultimately cell growth, cell proliferation, angiogenesis and cell survival. mTOR is the only currently known target of everolimus (Reviewed in Boulay and Lane, 2007)¹. mTOR is downstream of PI3K/AKT pathway, a pathway

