Nine patients were enrolled in the phase I portion of this study. Two patients on dose level 0 (pazopanib 600 mg daily and everolimus 5 mg daily) experienced dose limiting toxicities (grade 3 rash and pruritus and grade 3 thrombocytopenia requiring a dose reduction). Therefore, three patients were treated at dose level -1 per protocol. None of these three patients experienced a protocol-defined dose-limiting toxicity. Therefore, another three patients were treated at dose level -1 (pazopanib 400 mg daily and everolimus 5 mg daily) without any dose-limiting toxicities. Therefore, per protocol, dose level -1 was defined as the maximum tolerated dose.

Toxicity	Maximum Grade			
	G1	G2	G3	G4
Febrile neutropenia	-	-	1	-
Neutropenia	1	-	-	-
Thrombocytopenia	3	1	1	-

Hematologic toxicities (see table above) included febrile neutropenia (11%), neutropenia (11%), thrombocytopenia (56%), and anemia (36%). Grade 3 febrile neutropenia and thrombocytopenia each occurred in 1 patient. Non-hematologic toxicities were varied, though many were expected based on the known toxicities of everolimus and pazopanib. One patient did experience a grade 3 pneumothorax, which was possibly related to study therapy. Other non-hematologic toxicities included anorexia (11%), bone pain (11%), diarrhea (22%, 11% G3), fatigue (56%), dysgeusia (11%), headache (11%), hypertension (22%), mucositis (33%), musculoskeletal (muscle stiffness after prolonged periods of sitting, 11%), nausea (44%), palmo-plantar erythrodysesthesia syndrome (11%), pneumonia (11% G3), pruritus (11% G3), rash (33%, 11% G3), vomiting (33%), and weight loss (11%). Toxicities noted in laboratory evaluations were generally consistent with what is expected with both agents administered separately. G3 and 4 laboratory toxicities included increased ALT, hypophosphatemia, and hypouricemia each in 1 patient, and increased lipase in 2 patients.

Treatment was generally well tolerated at the MTD. Two of 6 patients came off treatment after 2 cycles because of toxicity. The others stopped treatment due to disease progression or physician decision.

Antitumor activity

Encouraging antitumor activity was noted in the bladder cancer patients treated on pazopanib and everolimus. Of five urothelial cancer patients evaluable, 3 had stable disease for 4 months, 4 months and 5.5 months respectively. One patient had a complete response which lasted 14 months.

Tumor type	(n)	Best objective response

Bladder	5	3 SD, 1CR, 1 NE

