6.2.3 Management of non-infectious pneumonitis

Both asymptomatic radiological changes (grade 1) and symptomatic non-infectious pneumonitis (grade 2 = not interfering with activities of daily living or grade 3 = interfering with activities of daily living and oxygen indicated) have been noted in patients receiving everolimus therapy. Non-infectious pneumonitis has been associated with everolimus and other mTOR inhibitors (Atkins 2004). In order to monitor for asymptomatic (grade 1) pulmonary infiltrates, a chest X-ray is required if a CT scan of chest is not used for bi-monthly disease evaluations. Additional chest CT scans may be performed, when clinically necessary. If noninfectious pneumonitis develops, a consultation with a pulmonologist should be considered. If the patient develops grade 3 pneumonitis, treatment with everolimus should be interrupted and the patient should be treated as medically indicated (short course corticosteroids, oxygen, etc). Management of non-infectious pneumonitis suspected to be associated with everolimus and dose modifications instructions are provided in Table 6.2.3.

Table 6.2.3 Management of non-infectious pneumonitis

Worst grade pneumonitis	Suggested investigations	Management of pneumonitis	everolimus dose adjustment
Grade 1	CT scans with lung windows and pulmonary function testing including: spirometry, DLCO, and room air O ₂ saturation at rest. Repeat chest x-ray/CT scan every 2 Cycles until return to baseline.	No specific therapy is required	No dose adjustment required for Pazopanib or everolimus. Initiate appropriate monitoring.
Grade 2	CT scan with lung windows. Consider pulmonary function testing includes: spirometry, DLCO, and room air O ₂ saturation at rest. Consider a bronchoscopy with biopsy and/or BAL. Monitoring at each visit until return to ≤ grade 1 or baseline. Return to initial monitoring frequency if no recurrence.	Symptomatic only. Consider corticosteroids and/or other supportive therapy if symptoms are troublesome.	Rule out infection and consider interruption of everolimus (and optional pazopanib) until symptoms improve to Grade ≤ 1. Re-initiate everolimus at one dose level lower. Discontinue everolimus if failure to recover within ≤ 28 days. Pazopanib may resume at the discretion of the treating physician and principal investigator once toxicity is recovered to ≤ Grade 1 even if everolimus is discontinued.

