14.1 Study Design/Endpoints

Phase I:

The primary endpoint is to determine the MTD and DLT's of the combination of everolimus and pazopanib. Safety and incidence of dose-limiting toxicities will be the primary outcome parameters. All patients in a dose cohort will complete 28 days (1 cycle) of combination treatment prior to the treatment of any patient at a higher dose level. If a patient does not complete the 28 days of treatment for reasons that are clearly not adverse events related to treatment, then that patient will be replaced, up to three per dose level. If more than three patients need to be replaced on a dose level, then the reasons will be re-evaluated before continuing. There will be no intrapatient dose escalation. Pazopanib and everolimus will be escalated according to the standard 3+3 Phase I methodology and dose escalation rules (described in detail in Section 5.3.1). Once it is documented that the last patient in a cohort has completed 28 days of

therapy without evidence of excessive dose limiting toxicity, approval will be requested from the DF/HCC DSMB for dose escalation to the next dose level will occur. Successive cohorts of patients will be accrued to determine the maximum tolerated dose that results in <33% dose-limiting toxicities with the combination of everolimus and pazopanib in patients with metastatic kidney cancer. Up to six patients will be treated at the MTD before proceeding to the expansion cohort.

The assessment of safety will be based mainly on the frequency of adverse events and on the number of laboratory values that fall outside of pre-determined ranges. Toxicities will be summarized as number and percent of patients, separately by dose cohort. Other safety data (e.g. electrocardiogram, vital signs, special tests) will be considered as appropriate.

Adverse events will be summarized by presenting, for each dose cohort, the number and percentage of patients having any adverse event, having an adverse event in each body system, and having each individual adverse event. Any other information collected (e.g. severity or relatedness to study medication) will be listed as appropriate. Descriptive statistics will be calculated to characterize the disease and previous treatment features as well as the details of protocol therapy. Toxicities will be tabulated by grade for each dose cohort and overall for all patients accrued to the Phase I study.

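### The expansion cohort's only specified toxicity incidence is for treatment-related grade 3-5 events; all-grade tables and rates of stopping for toxicity should be added

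*Combined protocol and SAP*

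**What the plan says.** Safety is a secondary objective of the expansion cohort (1.3.2.1), and the expansion text of 14.1 also names it in the primary objective.

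The Toxicity part of 14.4 then specifies three things:

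- An incidence table: "A summary of the incidence of all treatment-related grade 3-5 toxicities will be provided as maximum grade by toxicity type and body system".
- A listing: "Any other information collected (e.g. severity or relatedness to study medication) will be listed as appropriate".
- One overall rate: "Overall maximum grade 3 or higher treatment-related toxicity rates in all treated patients will be calculated". Its precision is illustrated by 90% intervals at four event counts, taking 29 as the number treated.

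For Phase I, 14.1 specifies more: the number and percentage of patients with any adverse event, by body system and by individual event, and in addition "Toxicities will be tabulated by grade for each dose cohort and overall for all patients accrued to the Phase I study". The expansion text does not repeat this.

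On treatment exposure, 14.4 plans descriptive statistics on how protocol therapy was given. It does not name interruption, reduction or discontinuation for toxicity.

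The data will exist. Section 11.3 has all adverse events recorded on case report forms, 12.1.2 schedules Adverse Event, Treatment and Off Treatment forms, and 5.8 requires the reason for removal to be documented.

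**The concern.** The grade 3 cut-off and the treatment-related filter together decide what a reader of the specified tables can see. By the protocol's own account, much of the toxicity of these drugs lies below the cut-off. Section 2.1.1 says: "Non-infectious pneumonitis has been reported with mTOR inhibitors but is commonly low-grade and reversible". Section 2.1.2.1 describes most of the common pazopanib events as grade 1 or 2.

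Events below the cut-off also change treatment under the protocol's own rules:

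- Grade 2 pneumonitis: interruption is considered, followed by "Re-initiate everolimus at one dose level lower" (Table 6.2.3).
- Grade 2 stomatitis: everolimus is interrupted (6.2.1).
- Intolerable grade 2 non-hematological toxicity: both drugs are interrupted, and a recurrence lowers both (6.3.1).
- Grade 2 thrombocytopenia: both drugs are interrupted (6.3.1).
- Grade 2 pulmonary or gastrointestinal bleeding, other than hemorrhoidal, and arterial thrombosis or ischemia of any grade: both drugs are discontinued (6.3.2).

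These rules are cited only to show that such events matter to exposure; nothing here questions them. A patient could lose drug, or leave treatment, because of a grade 2 event and add nothing to any specified rate. The trial may call the regimen promising on response, and its safety objective would then be answered with part of the picture. The result would also not line up with the all-grade Phase I report in section 2.3. The treatment-related filter narrows the tables further, and a single-arm trial has no control against which to check attribution.

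**Working it through.** **1. The plan's own figures.** Exact (Clopper-Pearson) two-sided 90% intervals for x events in n = 29 take the 5% quantile of Beta(x, n−x+1) and the 95% quantile of Beta(x+1, n−x).

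| x | Plan (14.4) | Recomputed |
|---|---|---|
| 0 | 0.0% to 9.8% | 0.0% to 9.8% |
| 2 | 1.3% to 20.2% | 1.2% to 20.2% |
| 4 | 4.9% to 28.9% | 4.9% to 28.8% |
| 6 | 9.4% to 36.8% | 9.4% to 36.8% |

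These agree within 0.1 percentage point. The issue is what is tabulated, not the arithmetic.

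**2. Share of affected patients below the cut-off.** Share omitted = (any grade − grade 3 or higher) / any grade.

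| Source | Any grade | Grade 3 or higher | Share omitted |
|---|---|---|---|
| Hypertension, pazopanib alone, n = 225 (2.1.2.1) | 41% | 9% (grade 3; no grade 4 figure given) | 32/41 = 78% |
| ALT elevation, same trial | 53% | 9% grade 3, under 1% grade 4 | 43/53 to 44/53 = 81% to 83% |
| Thrombocytopenia, Phase I combination, n = 9 (2.3) | 3 + 1 + 1 = 5/9 | 1/9 | 4/5 = 80% |

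In the same nine patients, fatigue (56%, 5/9), nausea (44%, 4/9), mucositis (33%, 3/9) and hypertension (22%, 2/9) carry no grade 3 mark, while diarrhea, pneumonia, pruritus and rash do. Reading no mark as no grade 3 event is an inference, though a reasonable one.

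**3. Scale in the expansion.** Assume the pazopanib-alone hypertension rates carry over to 29 treated patients:

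- any grade: 29 × 0.41 = 11.9 patients;
- grade 3: 29 × 0.09 = 2.6 patients;
- about 9.3 affected patients would be outside the grade 3-5 table.

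With the 25 patients that 14.2 gives as the maximum, the last figure is 25 × 0.32 = 8.0.

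**4. Stopping for toxicity.** Section 2.3 reports for the MTD: "Two of 6 patients came off treatment after 2 cycles because of toxicity". The rate is 2/6 = 33%, exact 90% CI 6.3% to 72.9%. In 29 patients that rate gives 29 × 2/6 = 9.7, and the interval limits give 29 × 0.063 = 1.8 to 29 × 0.729 = 21.1. Section 2.3 also says that none of these six patients had a DLT. It does not give the grades of the toxicities that ended treatment.

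**5. Can a grade 3-5 table be expected to show zeros?** At 9% grade 3 hypertension, P(0 of 29) = 0.91^29 = 0.065 and P(0 or 1) = 0.25. For an event with 0 of 9 at grade 3 in Phase I, the exact 90% upper limit is 28.3%. Zeros do not follow from either source.

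**The case against.** The strongest case against is that this is a narrow reporting matter. The plan promises a listing of other information, with severity as its first example, so low-grade events are not excluded. A table labelled grade 3-5 does not tell a reader that lower grades were absent. Descriptive statistics on how protocol therapy was given may well cover stops for toxicity: 14.1 uses similar wording for Phase I, and section 2.3 nevertheless reported the 2 of 6. Section 12.2 also allows unexpected events of grade 2 or higher to go to the safety committee.

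Part of this stands. The plan does not forbid the missing summaries, and the trial's own record suggests that some would be produced. But a listing is not a rate. In 14.1 the same listing sentence stands beside full all-grade tables, so the authors did not treat it as a substitute for them. The exposure wording permits a discontinuation count without promising one.

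Three stronger readings are tempting, and the documents do not support them.

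- A reader might infer that pneumonitis, mucositis and hypertension would be reported as zero or near zero. Section 2.1.2.1 gives 9% grade 3 hypertension and names it first among the most frequent grade 3 or 4 events. Section 2.1.1.6 calls grade 3 stomatitis the primary DLT of everolimus. No pneumonitis rate is given for this regimen. Nine Phase I patients, three of them at a higher pazopanib dose than the expansion uses, cannot establish near-zero rates.
- A reader might attach the 0.0% to 9.8% interval to a single harm with no grade 3 event. The table illustrates the overall grade 3 or higher rate; 14.4 plans no interval for each harm.
- A reader might infer that stopping for toxicity will go unreported. It may be described; what is missing is a specified rate.

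**Conclusion.** The point holds as a gap in the specified analysis. For the expansion cohort, the only toxicity incidence that 14.4 commits to is for treatment-related events of grade 3 or higher, and no rate of interruption, reduction or discontinuation for toxicity is specified. On the documents' own figures, the cut-off leaves out about four in five affected patients for hypertension, ALT elevation and thrombocytopenia.

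That size rests on three assumptions: that pazopanib-alone and nine-patient Phase I rates are a fair guide to the expansion; that hypertension above grade 3 was negligible where only grade 3 is given; and that the source figures can stand in for treatment-related events, although the common adverse events in 2.1.2.1 are reported regardless of causality. The existence of the gap depends on none of these.

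No endpoint, decision rule or monitoring step is affected. It is a cheap improvement that should be made because safety is a stated objective.

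**What to change.** In the Toxicity part of 14.4:

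1. Carry over the 14.1 approach. Tabulate maximum grade per patient by toxicity type and body system for all grades, once regardless of attribution and once for treatment-related events. Keep the present grade 3 or higher summary as a column.
2. Add the number and percentage, with 90% CI, of patients who interrupted, reduced or permanently discontinued either drug because of toxicity of any grade.

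The source is the existing Adverse Event, Treatment and Off Treatment forms. Section 11.2.1 counts laboratory abnormalities as adverse events only under conditions, so a footnote should say that laboratory rows follow that definition. Separate intervals at several grade thresholds for each harm group are not needed.

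The cost is plan wording and a few more tables, with no new data, visits or change to clinical management. The reported safety profile will look less favourable than a grade 3-5 table alone.

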14.5 Reporting and Exclusions

14.5.1 Evaluation of toxicity. Any participant who has received at least one dose of study therapy will be evaluable for toxicity. Patients who experience toxicity not meeting the definition of DLT but do not complete 28 days of study treatment will be replaced. Reasons for not completing 28 days of therapy will be reviewed.

14.5.2 Evaluation of response. All participants who received treatment will be assessed for response to treatment, even if there are major protocol treatment deviations. Patients who did not receive any dose of study medication will not be included in the analysis. Each participant will be assigned one of the following categories: 1) complete response, 2) partial response, 3) stable disease, 4) progressive disease, and unknown (not evaluable, insufficient data).

All conclusions should be based on all eligible and treated participants who received protocol therapy. Subanalyses will then be performed on the basis of a subset of participants, excluding those for whom major protocol deviations have been identified. However, these subanalyses will not serve as the basis for drawing conclusions concerning treatment efficacy, and the reasons for excluding participants from the analysis will be clearly reported. The 95% confidence intervals will be provided.

Pregnancy

Preclinical data regarding reproductive toxicity is described in the most recent Investigator Brochure. The potential reproductive risk for humans is unknown. Women of childbearing potential should be advised to use highly effective contraception methods while they are receiving everolimus and up to 8 weeks after treatment has been stopped.

To ensure patient safety, each pregnancy occurring while the patient is on study treatment must be reported to Novartis within 24 hours of learning of its occurrence. The pregnancy should be followed up to determine outcome, including spontaneous or voluntary termination, details of the birth, and the presence or absence of any birth

defects, congenital abnormalities, or maternal and/or newborn complications. The newborn will be followed for at least 12 months.

Pregnancy should be recorded on a Clinical Trial Pregnancy Form and reported by the investigator to the oncology Novartis Drug Safety and Epidemiology Department (DS&E). Pregnancy follow-up should be recorded on the same form and should include an assessment of the possible relationship to the study treatment and any pregnancy outcome. Any SAE experienced during pregnancy must be reported on the SAE Report Form.

